- the Declaration of Helsinki - Ethical Principles for Medical Research Involving Human Subjects; last revision Fortaleza, Brazil, October 2013
- the DIN EN ISO 14155
- Guideline for good clinical practice E6(R1)
- the German Medical Device Act, MPKPV
- §20 German Medical Device Act

The study will be started only in the case that a favorable opinion of the responsible Ethical Committee (EC), the Bundesamt für Strahlenschutz (BfS) and a successful request for waiving the authorization of the clinical trial to the Competent Authority (CA) has been obtained.

The information contained in this document, especially unpublished data, is the property of seca gmbh & co. kg. It is provided for the use of the investigator, potential investigator or consultant for review by you, your staff and an applicable Ethics Committee (EC) / Competent Authority. It is understood that this information will not be disclosed to others without written authorization from seca gmbh & co. kg.

seca	Clinical Investigation Plan Inv. code: BCA-12 Doc. code: 25-02-02-456	Rev. date: 16-01-19 Revision: 1.4 Page: 6 of 32
-------------	---	---

STUDY SYNOPSIS

Title of study:	Generation of prediction equations to analyze body composition of the elderly based on Bioelectrical Impedance Analysis (BIA)
Study code:	BCA-12
Study purpose:	The study is based on the clinical trial BCA-01 (AZ 111/11) "Generation of prediction equations to analyze body composition of obese adults based on Bioelectrical Impedance Analysis (BIA)" and implicates an extension of the study collective.
Objectives:	
The objective of the study is to develop prediction equations for calculating Fat-Free Mass FFM, Total Body Water TBW, Extracellular Water ECW, Visceral Adipose Tissue VAT, total Skeletal Muscle Mass SMM and segmental SMM in a group of elderly. The prediction equations are based on linear regression analysis between the gold standard reference methods Air Displacement Plethysmography ADP, Dual-energy X-ray Absorptiometry DXA, Magnet Resonance Imaging MRI, Deuterium dilution method (D2O) and Sodium Bromide dilution method (NaBr) on the one hand and bioelectrical impedance measurements on the other hand.
 
Multi-frequency bioimpedance is measured for all body segments: right arm, left arm, right leg, left leg, trunk, right body side and left body side using the seca mBCA 515 and 555 in standing position and the seca mBCA 525 in standing and lying position.

Study design:	Population based cross-sectional observational study
Study population:	150 elderlys (>60 years): community dwelling or living in old nursing homes
Entry criteria:	
Inclusion criteria
 
male and female subjects older than 60 years, stable medication (no changes during the past 6 months) subjects need to be able to sign the informed consent and privacy policy

Exclusion criteria

acute disease
 intake of diuretics
 wearing of support stockings
 edema diagnosed by inspection and palpation of lower limbs
 paralysis e.g. after a stroke
 neurodegenerative diseases e.g. ALS
 tumors in treatment
 amputation
 electronic implants e.g. pacemaker
 under the skin applied injection systems (e.g. insulin pumps or pain pumps)
 probands who cannot provide an ICF by themselves
 probands who might be dependent from the sponsor or the investigation site
 current alcohol abuse
 active prostheses
 electronic life-support systems, e.g. artificial heart, artificial lung
 portable electronic medical devices, e.g. ECG devices or infusion pumps
 metallic implants
 cochlea implants und heart valves prothesis (e.g. Starr-Edwards-Prothesis)
 vessel clips in the brain or medulla applied before 1995
 defeatable pumps
 catheter
 iron or metallic parts in the body (e.g. shard of metal)
 dental braces
 magnetic tooth implants
 not removeable piercings
 extensive tattoos

Study treatments: Treatment will not be executed.

Study conduct: Each subject will undergo the following examinations:

- 1 height measurement
- 1 body composition measurements in standing position with the seca mBCA 515
- 1 body composition measurements in standing position with the seca mBCA 555
- 1 body composition measurements in standing position with the seca mBCA 525
- 1 body composition measurements in supine position with the seca mBCA 525
- 1 DXA measurement
- 1 whole body MRI scan
- 1 ADP measurement
- 2 blood drawings
- 3 hand grip strength measurements

Study statistics: The biometric sample size calculation for the previous study BCA-01 (AZ 111/11) was carried out by the Coordination Centre for Clinical Studies (KKS) of the Charité, [name], [name], Germany under the direction of [name]. The study BCA-01 included subjects from 18 to 65 years.

For target variable measurement resistance of the left body side (RI 50 kHz) was chosen. This provides, according to preliminary tests done by the investigator, the best approach to gain the most relevant

seca	Clinical Investigation Plan Inv. code: BCA-12 Doc. code: 25-02-02-456	Rev. date: 16-01-19 Revision: 1.4 Page: 8 of 32
-------------	---	---

medical results for formula generation. The precision (confidence interval width for μ) of all other variables was varied in a way that maximum (superior sample size) will always be found in the resistance measurement of the left body side (RI 50 kHz) being crucial for formula generation.

The resulting sample size to generate a formula was $N = 124$ in the study BCA-01.

This number of 124 subjects is the basis for the calculation of the sample size in the current study BCA-12 for formula generation in older people.

The smaller age range that shall be examined in comparison to study BCA-01 is opposed to a greater change in body composition with high age. So no adaptation of sample size for these reasons is planned.

To achieve an overlap in the age range with the previous study BCA-01 additional 26 subjects between 60 and 65 years shall be examined.

The resulting sample size to generate a formula for elderly is $N = 150$.

This number allows a homogenous age distribution from 60 - 80 years. Older subjects will be examined as far as they can be recruited.

The prediction equations shall be developed by stepwise multiple regression analysis.

ABBREVIATIONS AND DEFINITION OF TERMS

ADP	Air Displacement Plethysmography
ADI	Acceptable Daily Intake
AE	Adverse Event
BCA	Body Composition Analysis
BfArM	Federal Institute for Drugs and Medical Devices
BfS	Federal Office for Radiation Protection
BIA	Bioelectrical Impedance Analysis
BM	Bone Mass
BMI	Body Mass Index
CI	Clinical Investigation, synonym term is "clinical study" or "study"
CIP	Clinical Investigation Plan, synonym term is "study protocol" or "protocol"
CRF	Case Report Form
D ₂ O	Deuterium
DIN	German Industrial Norm
DXA	Dual-Energy X-Ray Absorptiometry
ECW	Extra Cellular Water
FM	Fat Mass
FFM	Fat Free Mass
ICF	Informed Consent Form
ICW	Intra Cellular Water
IRMS	Isotopic Ratio Mass Spectrometry
KKS	Coordination Center for Clinical Studies
LST	Lean Soft Tissue
mBCA	medical Body Composition Analyzer
MDD	Medical Device Directive
MPKPV	Medical Device Clinical Investigation Regulation
MRI	Magnet Resonance Imaging
NaBr	Sodium Bromide
NOEL	No-Observed Effect Level
R	Resistance
SAE	Serious Adverse Events
SMM	Skeletal Muscle Mass
TBW	Total Body Water
UV	Ultra Violet
V	Volume
VAT	Visceral Adipose Tissue
XRF	X-Ray Fluorescence Spectroscopy
Z	Impedance

seca	Clinical Investigation Plan Inv. code: BCA-12 Doc. code: 25-02-02-456	Rev. date: 16-01-19 Revision: 1.4 Page: 10 of 32
-------------	---	--

CIP REVISION HISTORY

Revision number	Revision date	Explanation	Comment
1.0	05-12-17	First revision	
1.1	29-01-18	Handgrip strength measurement has been added for quality assessment of muscle mass	Changes in chapter 2.7 Procedure
1.2	07-05-18	
According to the feedback from the ethical committee on April 17, 2018 and a meeting between [name] and the ethical committee on April 24, 2018 the following changes were made:
 
 • Radiologist and commissioner for data security were added on page 4 • MRI specific exclusion criteria were added • Exclusion criteria "heart or kidney insufficiency" was changed to "intake of diuretics" to avoid internistic pre-examinations • Time column was added to the examination schedule • Statistical method for data analysis was added 	Changes affect the synopsis, chapter 1.8 Requirements on study population, chapter 2.7 Procedure and chapter 3. Study statistics
1.3	23-10-18	
After consulting the laboratories in Jülich and Boston we agreed to reduce the dosages for D2O and NaBr as follows:
 
 • Before: 0,4g D2O per kg body weight and 0,05g NaBr per kg body weight • Now: 0,1g D2O per kg body weight and 0,04g NaBr per kg body weight 	Changes affect chapter 2.3 Reference Methods (page 19)
1.4	16-01-2019	New mBCA 555 is included	Changes affect chapters: 1.3 Regulatory Information (page 13); 2.2 Model for standing bioimpedance measurement: mBCA 555 (page 17); 2.8 Procedure (pages 23-24)

seca	Clinical Investigation Plan Inv. code: BCA-12 Doc. code: 25-02-02-456	Rev. date: 16-01-19 Revision: 1.4 Page: 11 of 32
-------------	---	--

CONTENT

1. INVESTIGATIONAL PLAN	13
1.1 Bioelectrical Impedance Analysis	13
1.2 Study Rationale	13
1.3 Regulatory Information	13
1.4 Study Objective	13
1.5 Study Design	14
1.6 Study Schedule	14
1.7 Requirements on study procedure	14
1.8 Requirements on study population	14
1.9 Subject Discontinuation Criteria	15
1.10 Study Discontinuation Criteria	15
2. INVESTIGATIONAL DEVICES	15
2.1 Model for standing bioimpedance measurement: mBCA 515	15
2.2 Model for standing bioimpedance measurement: mBCA 555	17
2.3 Model for supine bioimpedance measurement: mBCA 525	18
2.4 Reference Methods	19
2.5 mBCA Device Accountability	21
2.6 Recruitment	21
2.7 Consent	21
2.8 Procedure	22

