1. INVESTIGATIONAL PLAN

1.1 Bioelectrical Impedance Analysis

The use of bioelectrical impedance analysis (BIA) is widespread both in healthy subjects and patients. BIA allows the determination of the fat-free mass (FFM), skeletal muscle mass (SMM), fat mass (FM), extracellular water (ECW) and total body water (TBW) when using appropriate population, age or pathology-specific BIA equations and established procedures. BIA equations are based on validation studies where BIA is compared with reference methods such as Air Displacement Plethysmography (ADP), Dual-Energy X-Ray Absorptiometry (DXA), Magnetic Resonance Imaging (MRI) and isotope dilution. [1]

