1.5 Study Design

The study BCA-12 is a cross-sectional observational study.

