1.9 Subject Discontinuation Criteria

All subjects have the right to withdraw consent without prejudice at any time during the study. If a subject withdraws consent, the investigator should make a reasonable effort to determine the cause for withdrawal of consent. For these subjects, as well as for subjects who require permanent discontinuation from examination with the medical device, the investigator should make a reasonable effort to complete all required study procedures. All information should be documented in the subject's source data documents and on the Case Report Form (CRF). A subject who discontinues treatment will not be replaced. The subject's participation in this study should be permanently discontinued as a result of:

- formal withdrawal of informed consent
- investigator concludes that it is in the subject's best interest to discontinue study procedures
- presence of other medical conditions that prohibit continuation of study procedures
- subject is willingly or inadvertently non-compliant to any of the CIP procedures in the opinion of the investigator

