2. INVESTIGATIONAL DEVICES

The seca medical Body Composition Analyzer (mBCA) is mainly used in hospitals, medical practices and inpatient care facilities in accordance with national regulations.

The mBCA records weight, height and bioelectrical impedance measurements and automatically calculates parameters such as fat-free mass (FFM) which can be derived from them. The results are displayed in graphical form and assist the attending physician with the following medical issues:

- determining energy expenditure and energy reserves as a basis for nutritional advice
- assessing metabolic activity and the success of a training program, e.g. within the framework of rehabilitation or physiotherapy
- determining a patient's fluids status

The mBCA is not intended for use on children.

2.1 Model for standing bioimpedance measurement: mBCA 515

seca	Clinical Investigation Plan Inv. code: BCA-12 Doc. code: 25-02-02-456	Rev. date: 16-01-19 Revision: 1.4 Page: 16 of 32
-------------	---	--

Technical Data

General:

- Dimensions (W×H×D): 976 × 1,251 × 828 mm
- Display type: 8.4" touch-screen display, can be swiveled 180° to the left and right
- Power supply: Power adapter
- Voltage: 100 V – 240 V
- Interfaces: seca 360° wireless, USB 2.0, Ethernet
- Microsoft® Windows® compatible printer via seca 115 PC software

Bioelectrical Impedance Analysis:

- Measurement method: 8-point Bioelectrical Impedance Analysis
- Type of electrode: Stainless steel, three pairs of hand electrodes, two pairs of foot electrodes
- Measurement frequencies: 1; 1.5; 2; 3; 5; 7.5; 10; 15; 20; 30; 50; 75; 100; 150; 200; 300; 500; 750; 1,000 kHz
- Measurements: Impedance (Z), Resistance (R), Reactance (Xc), Phase angle (φ)
- Measurement range Impedance: 10 Ω to 1,000 Ω
- Measurement segments: Right arm, left arm, right leg, left leg, right half of body, left half of body, torso
- Measurement current: 100 µA
- Measurement time: max. 90 seconds for 19 frequencies

The seca mBCA 515 has an integrated calibrated scale with a maximum load of 300kg. More information about the technical data for the scale and technical modifications can be found at the instruction for use for doctors and assistants at chapter 13.

PC software seca analytics 115:

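### Does naming nursing-home residents in the synopsis oblige the plan to recruit them, analyse them separately or limit the scope of its equations?

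*Combined protocol and SAP*

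**What the plan says.** The synopsis describes the population as "150 elderlys (>60 years): community dwelling or living in old nursing homes" and the design as "Population based cross-sectional observational study". Section 1.5 leaves out the population-based label: "The study BCA-12 is a cross-sectional observational study". Nursing homes are mentioned nowhere else, including Sections 1.4 (objective), 1.8 (eligibility), 2.6 (recruitment), 2.8 (procedure) and 3 (statistics).

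Section 2.6 recruits by flyer at pharmacies, sport clubs and notice boards, and also from the site's subject pool and by public advertisement.

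The synopsis introduces its list of measurements with "Each subject will undergo the following examinations". The list includes standing measurements on the mBCA 515, 555 and 525 and a supine one on the 525. Section 4.1.2 mentions a short walk to the DXA and MRI facilities.

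Section 1.8 does not make ability to stand or walk an eligibility criterion. Section 1.9 lists among its reasons for discontinuation "subject is willingly or inadvertently non-compliant to any of the CIP procedures in the opinion of the investigator", and adds: "A subject who discontinues treatment will not be replaced".

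Section 3 sets N = 150, aims for an even age spread from 60 to 80 years, and plans stepwise multiple regression. It has no term, count or subgroup for setting.

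**The concern.** A prediction equation is only as good as its coverage of the people it will be used on. Section 1.1 says that BIA gives valid results "when using appropriate population, age or pathology-specific BIA equations and established procedures", and Section 2 says that the devices are "mainly used in hospitals, medical practices and inpatient care facilities". Naming residents in the synopsis suggests that the equations are meant for them too.

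The operational text points the other way. The named flyer sites suit mobile volunteers, three measurements require standing, subjects walk to two facilities, and someone who cannot stand might enter under Section 1.8 and then be discontinued under Section 1.9 without replacement. If few or no residents complete the study, a systematic error in that group could not be estimated, although the plan still names them. The supine 525 equation, which could in principle be used on people unable to stand, would rest almost wholly on people who can.

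**Working it through.** **The plan's own figure.** Section 3 takes 124 subjects from BCA-01 and adds 26 aged 60 to 65: 124 + 26 = 150. This reproduces the stated N. None of the 150 is allocated by setting, and no statement in the plan depends on such an allocation.

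**How many residents might enter.** The documents give no resident share. For an assumed share p among volunteers, the expected number is 150p and the chance of none is (1 − p)^150.

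| Assumed p | Expected residents | Chance of none |
|---|---|---|
| 1% | 1.5 | 0.221 |
| 3% | 4.5 | 0.010 |
| 5% | 7.5 | 0.0005 |

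Low numbers are plausible, but only under these assumptions.

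**What an unseen shift would cost.** Suppose residents differ from the fitted equation by d residual SD and none is in the fit. Their individual root mean squared error is then multiplied by √(1 + d²):

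- d = 0.25: 1.031, or 3% more
- d = 0.5: 1.118, or 12% more
- d = 1.0: 1.414, or 41% more

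The documents give no value for d. Section 1.8 already excludes diuretics, edema, support stockings, paralysis, neurodegenerative disease, metallic implants, catheters and inability to consent in person. These exclusions may bring eligible residents closer to eligible community subjects, so nothing supports the largest value.

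**What a resident target would buy.** With k residents among 150, the 95% half-width for a setting coefficient, in residual SD and ignoring correlation with other predictors, is 1.976 × √(1/k + 1/(150 − k)), where 1.976 is the t quantile on 148 df.

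| k | Half-width (residual SD) |
|---|---|
| 5 | 0.90 |
| 8 | 0.72 |
| 18 | 0.50 |
| 30 | 0.40 |

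At k = 18 the standard error is √(1/18 + 1/132) = 0.251. A 0.5 SD shift is then 0.5/0.251 = 1.99 standard errors, which gives power of about 51% (two-sided 5%, noncentral t). A 0.25 SD shift is 0.995 standard errors, with power of about 17%. Correlation between setting and age or other predictors would lower both. So the obvious target would often miss the shifts it is meant to reveal.

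**How much standing is involved.** Sections 2.1 to 2.3 give at most 90 seconds of measuring on the 515 and 30 seconds each on the 555 and 525, or at most 90 + 30 + 30 = 150 seconds. The 3- and 5-minute slots in Section 2.8 also cover software steps and data entry, although the standing 525 slot does begin by keeping the subject on their feet. Section 4.3 provides for assisting people with limited mobility, including from a wheelchair.

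**Which equations are exposed.** The 515 and 555 are standing analysers, so their equations cannot be used on people who cannot stand. On that point the sample and the users match. Only the supine 525 equation is open to use beyond the sample.

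**The case for a change.** The strongest case for a change is that the plan names a group, offers no dedicated route to reach it, and lists no item that records who belongs to it. If setting goes unrecorded, nobody can say later whom the equations represent. At an assumed share of 5%, the chance of reaching 18 residents without a dedicated source is about 0.0005. A recruitment source, one CRF item and a scope sentence would leave N at 150.

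Part of this stands. The synopsis and Section 2.6 do not match well, few residents may be enrolled, and the supine 525 equation will rest mainly on people able to stand. The finished equations should be read with that in mind.

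The rest is weaker. The CRF is not among the documents, so it is unknown whether setting is already recorded. Treating inability to stand as non-compliance under Section 1.9 is an inference: that section leaves the judgement to the investigator and asks for reasonable effort to complete the remaining procedures, and Section 7.2 requires CRFs for subjects who do not finish. Section 2 describes general use of the devices and does not set the scope of these equations. A cut-off at 18 would label a fit containing 17 residents as community-only, and no decision would follow from the coefficient. Section 9.1 also requires a written amendment and ethics approval before any change takes effect.

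**Conclusion.** No change is needed. The synopsis says who may enter, Section 2.6 bars no resident, and the plan makes no promise about residents that its analysis fails to keep. Reporting numbers by setting, stating that the equations apply to the kind of people recruited, and noting how subjects who could not stand were handled are details that analysts would supply when describing the sample. The population-based label, absent from Section 1.5, is a clerical slip that affects no calculation. A resident target is a debatable trade-off: 18 of 150 gives ±0.50 residual SD and about even odds of detecting a 0.5 SD shift.

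The possible cost of leaving the plan as it is would be 3% to 12% more individual error in residents, for assumed shifts of 0.25 to 0.5 SD with no resident in the fit. Because only the supine 525 equation can be used on people who cannot stand, the cost of not sampling such people falls on that equation alone. The shifts and resident shares are assumptions, and the documents support no particular value.

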1. INVESTIGATIONAL PLAN

1.1 Bioelectrical Impedance Analysis

The use of bioelectrical impedance analysis (BIA) is widespread both in healthy subjects and patients. BIA allows the determination of the fat-free mass (FFM), skeletal muscle mass (SMM), fat mass (FM), extracellular water (ECW) and total body water (TBW) when using appropriate population, age or pathology-specific BIA equations and established procedures. BIA equations are based on validation studies where BIA is compared with reference methods such as Air Displacement Plethysmography (ADP), Dual-Energy X-Ray Absorptiometry (DXA), Magnetic Resonance Imaging (MRI) and isotope dilution. [1]

1.2 Study Rationale

The study is based on the clinical trial BCA-01 (AZ 111/11) "Generation of prediction equations to analyze body composition of obese adults based on Bioelectrical Impedance Analysis (BIA)" and implicates an extension of the study collective.

1.3 Regulatory Information

The seca mbca are non-invasive medical devices class IIa in accordance with rule 10 of the MDD 93/42/EEC Annex IX. While the seca mBCA 515 and 525 are CE approved (CE 0123), the mBCA 555 will be applied without CE mark.

This Clinical Investigation (CI) will be conducted in accordance with

- ⇒ the Declaration of Helsinki - Ethical Principles for Medical Research Involving Human Subjects; last revision Fortaleza, Brazil, October 2013
- ⇒ the DIN EN ISO 14155
- ⇒ Guideline for good clinical practice E6(R1)
- ⇒ the German Medical Device Act, MPKPV
- ⇒ §20 German Medical Device Act

The study will be started only in the case that a favorable opinion of the responsible Ethical Committee (EC), the Bundesamt für Strahlenschutz (BfS) and a successful request for waiving the authorization of the clinical trial to the Competent Authority (CA) has been obtained.

1.4 Study Objective

The objective of the study is to develop prediction equations for calculating Fat-Free Mass (FFM), Total Body Water (TBW), Extracellular Water (ECW), Visceral Adipose Tissue (VAT), total Skeletal Muscle Mass (SMM) and segmental SMM in a sub-group of elderly persons. The prediction equations are based on linear regression analysis between the gold standard reference methods Air Displacement Plethysmography (ADP), Dual-energy X-ray Absorptiometry (DXA), Magnet Resonance Imaging (MRI), Deuterium dilution method (D_2O) and Sodium Bromide dilution method (NaBr) on the one hand and bioelectrical impedance measurements on the other hand.

Multi-frequency bioimpedance is measured for all body segments: right arm, left arm, right leg, left leg, trunk, right body side and left body side using the seca mBCA 515 and 555 in standing position and the seca mBCA 525 in lying position.

seca	Clinical Investigation Plan Inv. code: BCA-12 Doc. code: 25-02-02-456	Rev. date: 16-01-19 Revision: 1.4 Page: 14 of 32
-------------	---	--

